8.2.2 Qualifying Symptoms of Suspected COVID-19

To identify suspected cases of COVID-19, prespecified symptoms as well as time criteria will be elicited from participants. Any participant who presents with a new onset or marked worsening of any one of the 15 targeted COVID-19 symptoms listed in the Symptom Diary (described in Section 8.2.1) persisting or recurring over a period of at least 24 hours (except

the symptoms of feeling hot or feverish, cough, shortness of breath, loss of taste, or loss of smell, which can be present for any duration) should be assessed by the investigator or medically qualified designee at a COVID-19 Confirmation Visit (see Section 8.2.3).

8.2.3 Scheduling Requirements and Procedures at a COVID-19 Confirmation Visit

The COVID-19 Confirmation Visit should be scheduled to occur as soon as possible, but within 3 days of symptom onset. If the 3-day window is exceeded, then the Confirmation Visit should be scheduled to be conducted as soon as possible. Every attempt should be made to assess the participant. If circumstances do not support a clinic visit, a home visit or visit to an alternate study site may be used, if allowed by local regulations. In the case of a home visit or visit to an alternate study site, all indicated study procedures should be performed, including NP swab collection (Section 8.2.4) for SARS-CoV-2 RT-PCR testing at the central laboratory. A participant may have more than one COVID-19 Confirmation Visit.

The COVID-19 Confirmation Visit must be performed by the investigator or medically qualified designee.

The following procedures are to be performed at a COVID-19 Confirmation Visit in any setting (eg, clinic, home, or alternate site visit) to assess the participant for COVID-19:

- 1. Confirm the presence or absence of symptoms of COVID-19. All COVID-19 symptoms that prompted the COVID-19 Confirmation Visit and/or are observed during the visit will be recorded on the appropriate eCRF.
- 2. An NP swab will be collected from the participant for central laboratory RT-PCR testing (see Section 8.2.4). If an additional sample is collected for local testing per local guidelines, the NP swab for central laboratory testing should be collected first.
- 3. A directed physical examination, vital signs measurement (including heart rate, blood pressure, respiratory rate, and temperature), and SpO2 (if device to measure SpO2 is available) to assess the participant's symptoms and severity of COVID-19.
- 4. Assess the participant for severity of COVID-19. See Section 8.2.10 for COVID-19 severity criteria.
- 5. Determine if further triage or clinical evaluation is needed, consistent with standard of care and local guidelines, and in conjunction with the participant's primary physician (if applicable).
- 6. The COVID-19 Confirmation Visit may be performed separately from the scheduled study visits in the SoA (Section 1.3.1) per the scheduling requirements described above. However, if a scheduled visit (Section 1.3.1) overlaps with the COVID-19 Confirmation Visit, all applicable procedures can be performed at the same visit.

If a participant was assessed for COVID-19 symptoms in a nonstudy outpatient or inpatient clinical setting (eg, outpatient clinic, Emergency Department, urgent care center, or hospital),

attempts should be made to obtain medical records from the outpatient facility or hospital for review by the investigator (or medically qualified designee). Relevant information (COVID-19 symptoms, local COVID-19 testing results, etc) should be recorded on the appropriate eCRF.

Study sites will follow infection control practices for encounters with participants presenting with suspected COVID-19 per local guidelines.

8.2.4 Nasopharyngeal Swab Collection for Viral Testing/Quantification

Study site personnel or their medically qualified designee will collect the NP swabs from participants and NP or OP swabs from index cases.

Swabs will be collected and tested as follows:

- For participants, NP swabs will be collected at the Day 1, Day 5, Day 14, and Day 29 study visits and at a COVID-19 Confirmation Visit (see below). At study entry (Day 1), the samples should be collected prior to the first dose of study intervention. Qualitative and quantitative SARS-CoV-2 RT-PCR testing at the central laboratory and SARS-CoV-2 genome sequencing for genetic lineage identification will be performed on the NP swabs. Testing for coinfection with other respiratory pathogens is also planned for the NP swabs collected from participants.
- For index cases, NP or OP swabs may be collected at screening (see Section 1.3.2). NP swabs are preferred; however, OP swabs are also acceptable for index cases only. This swab is separate from the sample for the first detectable SARS-CoV-2 test required for the index case prior to randomization of the participant(s) in the study (see Section 5.1). The swab is not required for study participation of household contacts; however, it is highly encouraged for complete virologic assessment. Qualitative and quantitative SARS-CoV-2 RT-PCR testing at the central laboratory and SARS-CoV-2 genome sequencing for genetic lineage identification will be performed on the NP or OP swabs collected at screening.

The swabs for collecting NP and OP samples will be provided by the central laboratory. The NP and OP swab sample collection, storage, and shipment instructions are provided in the laboratory manual.

Nasopharyngeal Swab Collection at a COVID-19 Confirmation Visit

NP swab samples should be collected from participants by study site personnel or their medically qualified designee within the time requirements for the COVID-19 Confirmation Visit (see Section 8.2.3). If an additional sample is collected for testing per local guidelines, the swab sample for central laboratory testing should be collected first.

If it is not possible to conduct the COVID-19 Confirmation Visit at the study site, as described in Section 8.2.3, the investigator may designate staff caring for the participant in an alternate nonstudy outpatient or inpatient clinical setting to obtain the samples.

The following procedures should be followed for obtaining an NP swab sample during a nonstudy outpatient or inpatient visit in a clinical setting (eg, outpatient clinic, Emergency Department, urgent care center, or hospital) other than the study site:

- 1. If a participant first visits a nonstudy outpatient or inpatient clinical setting other than the study site and is confirmed to have symptoms of COVID-19, the study staff should make every effort to obtain an NP sample using the study-supplied swab, as permitted, and the site should send this sample to the central laboratory for analysis.
- 2. If site staff are not permitted to access the outpatient facility or hospital to obtain an NP sample, they should coordinate with providers caring for the participant to use the study-supplied NP swab or equivalent to collect the sample for central laboratory testing, if possible.
- 3. If it is not possible to collect the NP swab sample with study-supplied NP swabs for central laboratory testing, the local SARS-CoV-2 test result should be collected.
- 4. If an NP sample cannot be collected at a nonstudy outpatient or inpatient clinical setting other than the study site, the sample should be collected using the study-supplied swab as soon as possible postvisit or postdischarge. The local SARS-CoV-2 test result and medical records should also be obtained from the outpatient facility or hospital.

8.2.5 SARS-CoV-2 RT-PCR Assay

NP swab samples collected from participants and NP or OP swab samples collected from index cases (Section 8.2.4) will be tested for the presence of SARS-CoV-2 RNA using the Roche Cobas SARS-CoV-2 PCR assay, which has been approved under EUA, at the central laboratory. This is a qualitative dual target assay that specifically amplifies a region in the SARS-CoV-2 ORF1 a/b as well as a conserved region in the E-gene for pan Sarbecovirus detection. The lower limit of detection for this assay is 1.8 × 10³ NDU/mL (RNA NAAT detectable units/mL). In addition, a second research-use only PCR assay, developed at Q-squared Genomics Laboratories, will be used to quantify SARS-CoV-2 RNA titers in NP samples. The SARS-CoV-2 Viral Load Quantitation Assay utilizes the MagMAXTM Viral/Pathogen Nucleic Acid Isolation Kit on the KingFisher system and reagents from the TaqPathTM COVID-19 Combo Kit to amplify 2 unique regions in the ORF1ab, N protein, and S protein genes. The lower limit of quantification is 500 RNA copies/mL and the upper limit of quantification is 500,000,000 RNA copies/mL.

Central laboratory RT-PCR assay results from NP swabs will be used for the analysis of efficacy. If extenuating circumstances impact the ability to use the central laboratory, results from a local laboratory will be used if available. If only OP swabs are available, the RT-PCR results will be used to support clinical endpoints and establish baseline viral status (ie, to establish whether they are in the primary analysis population, mITT-VN) but will not be used to assess virologic endpoints.

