4.2.1 Rationale for Endpoints

4.2.1.1 Efficacy Endpoints

The primary efficacy endpoint for the study, COVID-19 (laboratory-confirmed SARS-CoV-2 infection with symptoms), was selected in accordance with the US FDA guidance on development of drug and biological products for treatment or prevention of COVID-19 [Food and Drug Administration 2021]. Development of symptomatic disease represents a clinically meaningful endpoint for participants since it demonstrates the onset of deleterious effects they can directly perceive. A COVID-19 case for the study is defined as a participant with qualifying symptoms of COVID-19 with onset through Day 14 (for the primary endpoint) and SARS-CoV-2 detected by central laboratory RT-PCR testing from a sample collected at the COVID-19 Confirmation Visit. Laboratory-confirmed COVID-19 with onset through Day 29 will also be assessed as an exploratory endpoint. The onset of COVID-19 is determined by the day of onset of symptoms, rather than the day of the COVID-19 Confirmation Visit. Therefore, the day of onset of COVID-19 symptoms supports the primary endpoint, even if the day of the COVID-19 Confirmation Visit is later than Day 14. The qualifying symptoms of COVID-19 are provided in Section 8.2.2.

The study will evaluate SARS-CoV-2 RNA as a secondary endpoint through Day 14 (and as an exploratory endpoint through Day 29) to assess the impact of MOV on preventing viral transmission in participants with undetectable SARS-CoV-2 in baseline NP swabs. Viral transmission, even in the absence of symptoms, represents an important outcome with regards to infection control. This is best evaluated via RT-PCR detection of SARS-CoV-2 RNA since nucleic acid amplification offers the most sensitive method for assessment of viral transmission. For this reason, SARS-CoV-2 RNA has been selected as the appropriate endpoint.

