9.5 Analysis Populations

9.5.1 Efficacy Analysis Populations

The mITT will serve as the primary population for the analysis of efficacy data in this study. The mITT consists of all randomized participants who received at least 1 dose of study intervention. The primary objective will be assessed in the mITT-VN population, which consists of the subset of the participants in the mITT with undetectable SARS-CoV-2 in baseline NP swabs (ie, virus negative/undetectable at baseline). The mITT-VP population, consisting of the subset of the participants in the mITT with detectable SARS-CoV-2 in baseline NP swabs (ie, virus-positive/detectable at baseline) will be used in some of the exploratory analyses. Under certain extenuating circumstances (Section 8.2.5), eg, when only qualitative OP swab results are available from the central laboratory, qualitative OP swab results can be used to derive the baseline viral status.

A supportive analysis using the Per-Protocol population will be performed for the primary efficacy endpoint. The Per-Protocol population excludes participants from the mITT due to deviations from the protocol that may substantially affect the results of the primary efficacy endpoints. Participants with prophylaxis outcomes of "indeterminate" (Section 8.2.6) will be excluded from the Per-Protocol population. Moreover, participants who took <80% of the required doses will be excluded from the Per-Protocol population.

The final determination on protocol deviations, and thereby the composition of the Per-Protocol population, will be made prior to the final unblinding of the database and will be documented in a separate memo.

Due to the conflict in Ukraine, participants in Ukraine who were randomized in FEB-2022 with incomplete data for the primary endpoint (ie, no clinical outcome assessment on Day 14) will be excluded from the efficacy analyses in the mITT population.

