Percentage of participants who develop positive/detectable SARS-CoV-2 through Day 14 among those with undetectable SARS-CoV-2 in NP swabs at baseline	р	Stratified M&N method with CMH weights ^b	mITT-VN	M=C ^c
Percentage of participants who develop positive/detectable SARS-CoV-2 through Day 14 among those with undetectable SARS-CoV-2 in NP swabs at baseline	S	Stratified M&N method with CMH weights ^b	РР	Observed data only
Percentage of participants with detectable SARS-CoV-2 in baseline NP swabs developing COVID-19 by Day 14	р	Stratified M&N method with CMH weights ^b	mITT-VN	As described in 9.6.1
Percentage of participants with detectable SARS-CoV-2 in baseline NP swabs developing COVID-19 by Day 14	S	Stratified M&N method with CMH weights ^b	РР	Observed data only

C=case of COVID-19; CMH=Cochran-Mantel-Haenszel; M=missing; M&N=Miettinen and Nurminen; mITT-VN=modified intent-to-treat population with undetectable SARS-CoV-2 in baseline NP swabs; NP=nasopharyngeal; PP=per-protocol.

^a P=Primary approach; S=Supportive approach.

^b Miettinen and Nurminen method with CMH weights stratified by age and household size.

^c M=C is Missing considered as a case of COVID-19.

Participants in Ukraine who were randomized in FEB 2022 without clinical outcome assessment on Day 14 will be excluded from the efficacy analysis.

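### In the secondary Day 14 RNA-detection endpoint, a participant with no usable post-baseline NP result and only undetectable OP swabs is counted as a case

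*Combined protocol and SAP*

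**What the plan says.** Section 8.2.5 makes NP swabs the default: "Central laboratory RT-PCR assay results from NP swabs will be used for the analysis of efficacy". It then provides for the exception: "If only OP swabs are available, the RT-PCR results will be used to support clinical endpoints and establish baseline viral status". The same sentence closes the door on a third use, saying that such results serve those two purposes "but will not be used to assess virologic endpoints". Section 9.5.1 repeats the baseline allowance: "qualitative OP swab results can be used to derive the baseline viral status".

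Section 4.2.1.1 gives RNA detection its rank: "The study will evaluate SARS-CoV-2 RNA as a secondary endpoint through Day 14". Table 5 in Section 9.6.1 lists it as "Percentage of participants who develop positive/detectable SARS-CoV-2 through Day 14 among those with undetectable SARS-CoV-2 in NP swabs at baseline". Its primary approach is the stratified Miettinen-Nurminen comparison in mITT-VN with the code M=C, which the footnote explains: "M=C is Missing considered as a case of COVID-19". The supportive Per-Protocol row for the same endpoint carries the entry "Observed data only".

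**The concern.** The RNA-detection endpoint is a detectable/undetectable call. That is the same type of result that the plan accepts from an OP swab at baseline, where it decides who enters the denominator of this very endpoint. After baseline an OP result is barred, so the participant has no usable value, and the missing-data rule then supplies a positive one. A measured negative becomes an event.

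The bar also works in one direction only. A participant with an OP-detectable result and no NP result is a case either way, by the result or by imputation. On this endpoint the exclusion therefore removes no doubtful positives and can only convert negatives. What is at stake is the estimate of how far MOV prevents SARS-CoV-2 acquisition, which would be pulled toward no effect.

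**Working it through.** **Step 1: the rules side by side.** The documents give no rate, sample size or power for the RNA endpoint, so there is no stated figure to reproduce. The point rests on how the rules combine.

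- OP-only results have two permitted uses: clinical endpoints and baseline viral status (8.2.5). RNA detection regardless of symptoms is neither.
- Nothing in the plan treats a barred OP result as anything other than missing.
- Missing is a case for this endpoint (Table 5, primary approach). The footnote speaks of a case of COVID-19, which is not a category of an RNA endpoint; RNA-positive is the only workable reading.
- So a participant in mITT-VN with no usable NP result after baseline through Day 14, and only undetectable OP swabs, is scored as an event.

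**Step 2: where the rules stop giving an answer.** NP swabs are scheduled at Day 5 and Day 14, and at any Confirmation Visit (8.2.4). Table 5 does not say whether M=C applies to each visit or to the participant as a whole. A negative Day 5 NP swab followed by an OP-only Day 14 swab is therefore unresolved.

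**Step 3: size, on stated assumptions.** From the plan: 550 per arm in mITT-VN under balanced allocation (9.9.1). Assumed: true RNA rates of 12% (placebo) and 6% (MOV); a share m of each arm that is OP-only after baseline, equal in both arms and unrelated to true status; OP results that agree with true status. The documents give no value of m, so 1% and 3% are illustrations.

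All of the share m is scored positive, so each rate p becomes p + m(1 − p), and the difference becomes (1 − m) times the true difference:

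- placebo: 0.12 + 0.88m
- MOV: 0.06 + 0.94m

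Nominal power uses the normal approximation Φ[(d − 1.96·SE0)/SE1]. Here d is the difference in rates, SE0 is its pooled standard error and SE1 its unpooled standard error. As a check on the method, the same approximation at one-sided 0.0249 with 8% v 3.2% and 550 per arm gives 93.4% for the primary endpoint, against 93% in Table 7.

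| m | Placebo | MOV | Difference (points) | Risk ratio | Nominal power |
|---|---|---|---|---|---|
| 0 | 12.00% | 6.00% | 6.00 | 0.500 | 94% |
| 1% | 12.88% | 6.94% | 5.94 | 0.539 | 91% |
| 3% | 14.64% | 8.82% | 5.82 | 0.602 | 85% |

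For m = 3%: d = 0.0582, SE0 = 0.01940, SE1 = 0.01932, so (0.0582 − 1.96 × 0.01940)/0.01932 = 1.04 and power is 85%.

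In counts at m = 3%, 16.5 participants per arm are OP-only. Of these, 0.88 × 16.5 = 14.5 (placebo) and 0.94 × 16.5 = 15.5 (MOV) are false cases, against 66 and 33 true positives.

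**Step 4: sensitivity to the assumed rates.** Borrowing the plan's symptomatic rates of 8% v 3.2% as RNA rates, the difference goes from 4.80 to 4.75 points at m = 1% and 4.56 at m = 5%. The relative reduction goes from 60% to 53% and 36%.

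**The case against.** **The RNA endpoint may not be virologic.** The plan does not define the term. Sections 4.2.1.1 and 9.4.1 list RNA detection among the efficacy endpoints, and the Amendment 5 rationale calls OP results acceptable for efficacy endpoints. On that reading the bar covers only titer and sequencing, and nothing goes wrong. This reading is possible but weaker. Section 8.2.5 allows OP only for clinical endpoints and baseline status, and Section 4.2.1.3 discusses the transition to viral positivity under the Virology Endpoints heading. Either way a clarifying sentence is needed.

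**Not every negative OP swab becomes an infection.** A reader might infer that any OP-only visit produces a false case. The documents do not support that. The result is certain only when no usable NP result exists after baseline through Day 14; other patterns are undefined.

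**The effect on the plan's own scale is small.** Miettinen-Nurminen as used here estimates a risk difference, which shrinks only by the factor (1 − m). This stands. The larger movement in the risk ratio should not be read as the loss on the planned estimate. Nominal power still falls because the added false cases raise the variance. But Section 9.8 assigns alpha only to the primary hypothesis and the all-participant Day 14 hypothesis, so that power has no confirmatory meaning.

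**It is rare and there is a check.** OP use is meant to be exceptional, and the supportive Per-Protocol analysis does not impute. Both stand. That analysis also changes the population (for example, it drops participants who took under 80% of doses), so a difference between the two could not be traced to the OP rule alone.

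**Counting missing as failure is a conservative convention.** That is reasonable where nothing was measured. It is harder to defend where a result exists and the plan trusts the same type of result at baseline.

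**Conclusion.** The point holds in a limited form. In the primary approach to the Day 14 RNA-detection endpoint, the rules as written score a participant with no usable post-baseline NP result and only undetectable OP swabs as a case. They leave mixed NP/OP patterns undefined. The bias is toward no difference, and on the assumptions above it is about 0.06 to 0.18 percentage points on the planned risk difference for an OP-only share of 1% to 3%. The share, the RNA rates, the equality between arms and the agreement of OP with true status are all assumptions.

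A reader might go further and infer that the trial's main result is affected. It is not. OP results are usable for the primary endpoint, and Section 8.2.6 already counts participants who stay asymptomatic as successes whatever the swab shows. Nor do the documents show the same problem at Day 29. That RNA endpoint is exploratory, and Section 9.6 leaves its methods to the sSAP. This is a minor point that is cheap to settle before unblinding.

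**What to change.** - In 8.2.5, limit the bar on OP-only results to quantitative titer and sequencing endpoints. State that, when no NP result is available, the qualitative OP result is used for the Day 14 RNA-detection endpoint.
- In the Table 5 footnote, say that M=C for this endpoint applies at participant level, only when neither an NP nor an OP result exists, and that a case here means RNA-positive. State how a negative Day 5 NP swab with an OP-only Day 14 swab is scored.
- If M=C is used for the exploratory Day 29 RNA endpoint, carry the same rule into the sSAP.

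The cost is one sentence and one footnote. The endpoint is not confirmatory, so Section 9 allows the analysis change to be recorded in the sSAP before unblinding. The downside is that a few endpoint values would come from a different swab type, which the plan already accepts for baseline status and clinical outcome.

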8.2.6 Assessment of Prophylaxis Outcome

The clinical outcome of prophylaxis will be assessed at the Day 14 and Day 29 visits for all participants and at the COVID-19 Confirmation Visit for participants who develop laboratory-confirmed COVID-19 with symptoms (see Section 1.3.1). Assessments should be made according to the following definitions:

Term	Definition		
Clinical Success	The participant does not develop laboratory-confirmed COVID-19 with onset within the window of interest (ie, symptom onset on or before Day 14 for the Visit 4 assessment; and on or before Day 29 for Visit 6 assessment).		
	Note: Participants who remain asymptomatic through Day 14 (or Day 29, for the Day 29 endpoint) are also considered clinical successes regardless of SARS-CoV-2 results (positive, negative, or missing).		
Clinical Failure	The participant develops laboratory-confirmed COVID-19 with onset within the window of interest (ie, symptom onset on or before Day 14 for the Visit 4 assessment; and on or before Day 29 for Visit 6 assessment).		
	The date of onset is considered the date of onset of symptoms. Note: An assessment of "Clinical Failure" on or before Day 14/Visit 4 will also be carried forward to the Day 29/Visit 6 assessment.		
Indeterminate	The outcome is indeterminate if any of the following apply:		
	• The participant is lost to follow-up during or has discontinued from the study prior to the window of interest (ie, prior to Visit 4 or Visit 6 for the outcome assessments conducted at those visits).		
	Note: This definition does not apply to participants who developed laboratory-confirmed COVID-19 with symptoms prior to leaving the study. For those participants, prophylaxis outcome should be assessed as "Clinical Failure" per the definition above.		
	• Death unrelated to COVID-19.		
	• The participant is symptomatic and missing the required viral test for confirmation of COVID-19.		
	Note: A virus-detectable NP swab collected within +/-5 days of symptom onset is considered to be within an acceptable window to confirm onset of COVID-19. A virus-undetectable NP swab that is collected within 5 days after symptom onset is considered to be within an acceptable window to rule out COVID-19.		
	NP swabs collected outside these windows are considered missing.		
	• There are other extenuating circumstances that preclude classification as a clinical success or failure, such as:		
	- The participant receives Sponsor-designated treatment or preventative agents targeting SARS-CoV-2 for reasons other than rescue treatment for participants who develop COVID-19; see Section 6.5.		

Term	Definition
	 Clinical observations and diagnostic tests cannot distinguish COVID-19 from another confirmed diagnosis (eg, influenza like symptoms with detectable results for both influenza and SARS- CoV-2 diagnostic tests).

